14.6 Demographics, Medical History, Baseline Characteristics and Concomitant Medications

Demographics, baseline disease characteristics and medical history information will be summarized for the safety population by dose level in order to assess the comparability of the treatment groups descriptively. Data to be tabulated will include demographic features such as age, sex and race, as well as disease-specific characteristics.

The number and percentages of patients screened, treated, completed the treatment/study, and withdrawn from treatment/study for any reasons will be presented overall and by treatment group/dose level.

14.7 Pharmacokinetic Analyses

PK parameters for mirdametinib and PD-0315209 will be calculated using non-compartmental analysis with appropriate software such as Phoenix WinNonlin (Version 8.1 or higher, Certara, Inc.). Only plasma concentrations greater than or equal to the validated lower limit of quantitation (LLQ) will be used in the PK analyses. Actual blood sampling times will be used in all PK analyses. Per-protocol times will be used to calculate mean plasma concentrations for graphical displays.

The following PK parameters will be determined as appropriate:

C_{\max}	Maximum concentration, determined directly from individual concentration-time data (Cycle 1, Day 1 only)
$C_{\max, ss}$	Maximum concentration at steady-state, determined directly from individual concentration-time data (Cycle 1, Day 15 only)
$C_{\text{trough}, ss}$	Minimum concentration at steady-state, determined directly from individual concentration-time data (Cycle 1, Day 15 and Cycle 2, Day 1 only)
T_{\max}	Time to reach maximum concentration, determined directly from individual concentration-time data.
AUC_{last}	Area under the concentration-time curve from time-zero to the time of the last quantifiable concentration; calculated using the linear-up/log-down trapezoidal rule (Cycle 1, Day 1 only)
$AUC_{\text{last}, ss}$	Area under the concentration-time curve from time-zero to the time of the last quantifiable concentration at steady-state; calculated using the linear-up/log-down trapezoidal rule (Cycle 1, Day 15 only)

Additional PK parameters may be calculated if data allows. Population PK modeling may be performed on the mirdametinib concentration-time data collected from this study to quantitatively describe the PK, explore the PK variability, and identify any covariate effects such as demographic, intrinsic or extrinsic factors, or co-medication on the PK. The exposure-response relationship between measures of mirdametinib exposure and measures of efficacy, including, but not limited to, ORR, PFS, and DOR may also be explored. The relationship between mirdametinib exposure and key safety variables, including EKG, may be explored. In addition, tumor biopsy biomarkers may be explored in the exposure / response analyses.

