3.0 BACKGROUND AND RATIONALE

3.1 Mirdametinib

Mirdametinib is a highly selective and potent, non-ATP-competitive oral inhibitor of MEK1 and MEK2 kinases. It significantly inhibits the phosphorylation of the MAP kinases ERK1 and ERK2, leading to impaired tumor cell growth in vitro and in vivo with an IC50 of approximately 0.3 nM based on in vitro cellular assays and PK/PD of mouse xenograft

Memorial Sloan Kettering Cancer Center
[name]
[name]

tumor models. Mirdametinib has exhibited anti-tumor activity against a broad spectrum of human tumors in cell lines and animal xenograft models.

The plasma PK profile of mirdametinib is characterized by rapid absorption with the Cmax achieved by approximately 1-hour post-dose and bi-phasic elimination with a terminal elimination half-life ranging from 22 to 30 hours. Mirdametinib (PD-0325901) is largely eliminated by conversion to a primary active metabolite (PD-0315209) which has a half-life ranging from 30 to 40 hours. Generally, exposure of mirdametinib (both Cmax and AU_{tau}) increases proportionally with increases in dose from 1 to 30 mg QD or BID. Mirdametinib exposure following multiple doses exhibited a small degree of accumulation exhibiting accumulation ratios for AU_{tau} ranging from 1.3 to 1.9 after 21 days of BID dosing. Accumulation of the primary metabolite, PD-0315209, was higher at approximately 3-fold.

Mirdametinib is a substrate of CYP3A4, CYP1A2, CYP2C9 and CYP2C19, however, conversion of mirdametinib to the primary metabolite PD-0315209 is largely mediated by non-CYP enzymes. Therefore, inhibition of CYP enzymes is unlikely to significantly alter the pharmacokinetics of mirdametinib. Mirdametinib is a substrate of both P-gp and BCRP. Inhibition of P-gp may increase the absorption of mirdametinib. However, in the absence of P-gp inhibitors, mirdametinib is extensively and rapidly absorbed due to its high permeability and solubility. Only small amounts of mirdametinib are eliminated in urine and feces unchanged. Therefore, inhibition of P-gp is not likely to have a significant impact on the systemic exposure of mirdametinib. Mirdametinib is not a significant inhibitor of CYP enzymes or major drug transporters with the exception of OAT1 which may be inhibited at clinically relevant concentrations.

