4.2 Intervention

Study Periods

Each subject will undergo 3 periods (screening, treatment, and post-study follow-up).

Screening

The screening period will be from the signing of the informed consent until the first dose of the first study drug on Day 1 of Cycle 1 (C1D1). The screening period should not exceed 28 calendar days before C1D1.

Treatment

A treatment cycle lasts 28 days. The treatment period will be from the first dose of the first study drug until the last dose of the last study drug.

The treatment will continue until the disease progression, death, unacceptable toxicity, withdrawal of consent, or another reason for permanent discontinuation of treatment.

Patients with documented progression of disease may be allowed to continue on study if the patient is tolerating treatment, and in the opinion of the investigator, the patient is deriving clinical benefit from continuing study treatment and continuation of treatment is approved by the principal investigator. If said patient continues treatment post progression, they will require reconsent.

Dose levels of mirdametinib are summarized in section 10.2.

Post-study Follow-up

The post-study follow-up will include the end of treatment (EoT) visit, the safety follow-up visit, and the long-term follow-up.

An End of Treatment (EoT) visit will be performed within 7-14 days after the administration of the last dose of the last study drug.

The safety follow-up (FU) visit will be performed 30 days after the last dose of the last study drug treatment (except for subjects who died, withdrew consent, and objected to further data collection or were lost to follow up). The safety FU assessment can be done via the clinic visit (recommended) or via a phone call (if subject cannot attend the clinic visit or has started a new anti-cancer treatment). The investigator may order unscheduled FU visits after the 30-day safety FU visit if the adverse events ongoing at the safety FU are deemed to be clinically significant and related to the study drug(s).

The long-term follow-up will aim to obtain the information necessary for the duration of response (DOR) and the progression-free survival (PFS) endpoints. The long-term follow-up visits will be performed via clinic visit or phone call about every 3 months for 12 months

Memorial Sloan Kettering Cancer Center
[name]
[name]

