10.1 Mirdametinib Study Treatment

- Subjects will be instructed to take mirdametinib at home and record the time of intake for both daily doses in the patient dosing diary. Missed doses will also be recorded in the dosing diary. Subjects will be instructed to **not** take their planned morning dose of mirdametinib prior to each study visit during the treatment period. Instead, the morning dose will be taken following the pre-dose PK blood draw or any other assessment scheduled to be obtained at pre-dose during the visit.
- Mirdametinib treatment will be dispensed to subjects every two Cycles during scheduled study visits as described in the SoA or at an unscheduled visit if mirdametinib treatment is damaged/lost.
- Throughout the treatment period, subjects will self-administer study treatment BID utilizing a continuous dosing schedule in 28-day Cycles.
- Subjects will be instructed to swallow capsules whole and not to open or chew them prior to swallowing.
- No capsule should be ingested if it is broken, cracked, or otherwise not intact.
- Subjects should be encouraged to take their dose approximately every 12 hours
- Subjects can take mirdametinib capsules without regard to food intake.
- Delivery of mirdametinib via nasogastric tube or gastrostomy tube is not allowed.
- If a subject misses a scheduled dose of study treatment, and it is within 6 hours of the scheduled dose, the subject should immediately administer the missed dose and resume study treatment in accordance with the normal administration schedule. If more than 6 hours has elapsed since the time of scheduled administration, the subject will **not** be instructed to administer the missed dose and to resume study treatment as prescribed.
- Subjects should not take 2 doses together to “make-up” for a missed dose.
- If a subject vomits any time after taking a dose, then they must be instructed not to take another dose to “make up” for vomiting, but rather, to resume subsequent doses as prescribed.

Memorial Sloan Kettering Cancer Center
[name]
[name]

- If a subject inadvertently takes 1 extra dose, then the subject should not take the next scheduled dose of study treatment. Only one dose should be skipped in this context.

The dose levels for mirdametinib are summarized as follows:

Dose Level -2INT	2mg PO BID, 3 weeks on/1 week off
Dose Level -2	2mg PO BID given continuously
Dose Level -1INT	3mg PO BID, 3 weeks on/1 week off

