 - a. Day 1 and Day 15 of Cycle 1: pre-dose and at 0.5h, 1.0h, 2.0h and 4.0h after the mirdametinib dose
 - b. Day 1 of Cycle 2: pre-dose
7. **Ophthalmological exam:** must include visual acuity, tonometry, slit lamp exam and optical coherence tomography (OCT); fundoscopy with pupil dilation is not mandatory but may be performed at the discretion of the ophthalmologist. For cycles that do not have a scheduled ophthalmological exam, the treating physician will evaluate the participant for ocular toxicity and refer them to an ophthalmologist if clinically indicated.
8. **LVEF assessment by echocardiogram (Echo),** where the exam may be limited only on the measurement of LVEF without other aspects (global and regional contractility, stroke volume etc.), unless requested at the investigator's discretion. Results from a MUGA scan can also be used if it is performed as part of the patient's routine care.
9. **Imaging** to be performed within five-day window up to cycle 12, then within 7-day window for cycles 12 and above
10. **Paired tumor on-treatment biopsy – Core Biopsy (Optional).** If tumor lesion is accessible at acceptable risk and the patient has consented, the core biopsy will be obtained from the primary or metastatic tumor within 7 days before C2D1.
11. Clinical/local lab tests are listed in Table 2
12. The triplicate ECG will be done pre-dose and at 4 hours post-dose on C1D1 and C2D1. All other triplicate ECGs will be obtained pre-dose.
13. The long-term follow-up visits may be done in clinic or via telehealth
14. Baseline characteristics of these patients will utilize laboratory and clinical studies performed on C1D1.
15. Laboratory Assessments and Urinalysis: must be completed within 3 days before dosing on Day 1 of each cycle except for on Cycle 1 Day 1 (which must be completed on same day)

Memorial Sloan Kettering Cancer Center
[name]
[name]

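### Section 14.7 labels the Cycle 2 Day 1 pre-dose sample a steady-state trough at every dose level, but at the two contingent 3-weeks-on/1-week-off levels it follows a week off drug

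*Combined protocol and SAP*

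**What the plan says.** - **Parameter definition (14.7).** Ctrough,ss is the "Minimum concentration at steady-state, determined directly from individual concentration-time data (Cycle 1, Day 15 and Cycle 2, Day 1 only"). The list opens with "The following PK parameters will be determined as appropriate", a general qualifier that is not tied to schedule.
- **Sampling (Schedule of Assessments, Table 3, PK footnote).** After the serial samples on Cycle 1 Days 1 and 15, there is one further sample: "Day 1 of Cycle 2: pre-dose". It is the same for all levels.
- **Schedules (4.2 and 10.1).** "A treatment cycle lasts 28 days". Dose Level -2INT is "2mg PO BID, 3 weeks on/1 week off" and Dose Level -1INT is "3mg PO BID, 3 weeks on/1 week off". All other levels are continuous.
- **Values below quantitation (14.7).** "Only plasma concentrations greater than or equal to the validated lower limit of quantitation (LLQ) will be used in the PK analyses". The documents do not give the LLQ.
- **Reporting (11.9.1).** Concentrations and PK parameters are summarised descriptively by dose level and by arm.
- **Elimination (3.1).** Mirdametinib has a "terminal elimination half-life ranging from 22 to 30 hours". The active metabolite PD-0315209 has a half-life of 30 to 40 hours.

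**The concern.** A trough at steady state is the concentration just before the next dose during uninterrupted dosing. At continuous levels both named visits meet that description. At -2INT and -1INT only Cycle 1 Day 15 does, because the Cycle 2 Day 1 sample comes at the end of the off week. The rule in 14.7 nevertheless names both visits for every level.

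Levels -2 and -2INT share the same milligram dose, as do -1 and -1INT. A table of Ctrough,ss by dose level would therefore show a large difference at Cycle 2 Day 1 that reflects the off week and says nothing about exposure during treatment. Investigators review the available PK data at each 3+3 step, and 14.7 allows exposure-response work, so the label could travel further than one table. If an intermittent level became the RP2D, the same rule would apply to the expansion cohorts, which Section 4.2 sizes at up to 28 subjects each in Arm 1 and up to 30 each in Arm 2.

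**Working it through.** The plan states no figure on this point, so there is nothing to reproduce. The check is whether the Cycle 2 Day 1 concentration could pass for a trough.

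**Timing.** Take the off week as Days 22-28. This is the plain reading, but the documents do not name the off days. The last dose is then the evening of Day 21, and the last true trough is 12 h later, on the morning of Day 22. The Cycle 2 Day 1 pre-dose sample falls on Day 29, which is 7 x 24 = 168 h after that trough.

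**Decay.** Fraction of the steady-state trough left = 2^(-168/half-life).

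| Analyte | Half-life (3.1) | Half-lives in 168 h | Left at C2D1 |
|---|---|---|---|
| Mirdametinib | 22 h | 7.64 | 0.5% |
| Mirdametinib | 30 h | 5.60 | 2.1% |
| PD-0315209 | 30 h | 5.60 | 2.1% |
| PD-0315209 | 40 h | 4.20 | 5.4% |

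**Cross-check.** Section 3.1 reports parent accumulation ratios of 1.3 to 1.9 on BID dosing. The implied effective half-life is -12 x ln 2 / ln(1 - 1/R), or 5.7 to 11.1 h, which would leave less than 0.01% of the parent trough. For the parent, the table is therefore the cautious case.

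**Visit window.** Section 11.2 allows on-treatment visits to move by 3 days. If the last dose stays on Day 21 and the Cycle 2 visit comes 3 days early, the interval is 96 h. That leaves 4.9-10.9% of the parent trough and 10.9-19.0% of the metabolite trough. The sample is still not a trough.

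**Effect on Ctrough,ss.** This depends on how the two visits are combined, which the plan does not say. With the Day 15 trough set at 100%:
- Reported by visit: Day 15 is unaffected, and only the Cycle 2 Day 1 value is wrong.
- Arithmetic mean (assumed): (100 + 0.5)/2 = 50.3% to (100 + 5.4)/2 = 52.7%.
- Lower of the two (assumed): 0.5% to 5.4%.

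**Is Day 15 sufficient alone?** It follows 14 days, or 336 h, of BID dosing. The fraction of steady state reached is 1 - 2^(-336/half-life), which is at least 99.96% for the parent (30 h) and at least 99.7% for the metabolite (40 h). It is a valid steady-state trough at the intermittent levels.

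**The case against.** Several parts of the case on the other side stand.

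- **Pooling is not stated.** A reader might infer that Ctrough,ss at the intermittent levels would be roughly halved. That requires averaging the two visits, and no section says so. Naming two visits can equally mean one trough per visit.
- **The LLQ rule does not add to the bias.** A reader might infer both that the low value pulls Ctrough,ss toward zero and that dropping low values biases what is left. A given sample cannot do both. If it is below the LLQ it is left out, and that patient's value rests on Day 15, which is the correct outcome. Selection affects only a separate Cycle 2 Day 1 summary, which would then consist of patients with higher residual concentrations.
- **Near zero is too strong as a general description.** It fits the parent. The metabolite keeps up to about 5% and may be quantifiable.
- **The parameter is not prominent.** Table 1 names AUC0-last, Cmax and Tmax but not a trough. Section 11.9.1 says only that the parameters may include Ctrough,ss, and exposure-response analyses are optional. Population PK modelling with recorded dose times could use an off-week sample without harm.
- **The levels may never open.** Level -2INT needs both the 4 mg and 2 mg BID continuous levels to fail in Arm 1. Level -1INT needs both the 4 mg and 3 mg BID continuous levels to fail in Arm 2, and de-escalation there is at the investigator's discretion.

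One part does not stand. The general qualifier at the head of the list, and the recording of actual sampling and previous-dose times, would let a careful analyst spot the problem. They do not tell the analyst to leave out a visit that the definition names.

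**Conclusion.** The point holds as a labelling error in a pre-specified definition. At -2INT and -1INT, 14.7 would report as a steady-state trough a concentration at about 0.5-2.1% (parent) or 2.1-5.4% (metabolite) of the true trough. This assumes Days 22-28 off, first-order decay at the half-lives in 3.1, and a visit on its nominal day. The error in Ctrough,ss as a whole cannot be sized from the documents: Day 15 is untouched if visits are reported separately, and a value of about 50-53% of the truth follows only if they are averaged.

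The point is minor. It is conditional on an intermittent level opening, and it concerns a descriptive parameter that Table 1 does not name. It affects no sample size, error rate or DLT decision rule. The documents do not show that any planned exposure-response analysis would use this parameter.

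**What to change.** In 14.7, state that for intermittent dose levels Ctrough,ss is taken from Cycle 1 Day 15 only, and that the Cycle 2 Day 1 pre-dose value is listed separately as an off-drug concentration. For continuous levels keep both visits and say that they are reported by visit, which also removes the doubt about pooling.

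The cost is one sentence. No sample, visit or dose changes, because Day 15 is already collected at every level. In the same revision, the administration text in 10.1 and the study-drug footnote to Table 3, which describe only continuous daily dosing, should be reconciled with the intermittent levels so that the timing of the Cycle 2 Day 1 sample relative to the last dose is explicit.

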14.8 Biomarker Analyses

For each patient in the study, blood and tumor tissue samples will be collected, evaluated and archived to support exploratory biomarker analysis. Gene mutations and other genomic features, and other exploratory biomarkers will be correlated with response.

As data warrants, exploratory analysis may be performed on each exploratory endpoint listed. In addition, exploratory analyses may be performed to examine the relationship between exposure to mirdametinib and clinical and safety endpoints (including tumor size or change in tumor size from baseline).

These translational endpoints will include biomarkers associated with response, such as pre-treatment and on-treatment MSK-IMPACT, and cell free DNA dynamics using MSK-ACCESS. MSK-IMPACT will be performed on all solid tumor biopsies, and MSK-ACCESS will be performed serially at timepoints specified in the Schedule of Assessments. These samples will be banked. Any prioritized findings arising clonally in tissue will be cross-validated in cfDNA from the same patient. In addition to confirming tissue findings, cfDNA sequencing will allow for (1) the assessment of response prior to imaging, (2) an analysis of the differential response of heterogenous subclones to treatment, and (3) the acquisition of sequencing data where tissue collection was not possible.

In parallel with the above, the solid tumor biopsies will be utilized for additional translational work, and this line of inquiry includes the generation of PDX models and/or tumor derived cell lines and transcriptomic and protein analyses.

15.0 TOXICITIES/RISKS/SIDE EFFECTS

Adverse Events

CTCAE Version 5 will be utilized for toxicity evaluation. An AE is the development of an undesirable medical condition or the deterioration of a pre-existing medical condition following or during exposure to a pharmaceutical product, whether or not considered causally related to the product. In clinical studies, an AE can include an undesirable medical condition occurring at any time, including baseline or washout periods, even if no study drug has been administered.

Memorial Sloan Kettering Cancer Center
[name]
[name]

The intensity and causality of each AE will be assessed by the investigator as outlined in the following sections.

- Grade 1: Mild; asymptomatic or mild symptoms; clinical or diagnostic observations only; intervention not indicated; easily tolerated
- Grade 2: Moderate; minimal, local, or noninvasive intervention indicated; limiting age-appropriate instrumental activities of daily living (ADLs). (Instrumental ADL refer to preparing meals, shopping for groceries or clothes, using the telephone, or managing money.)
- Grade 3: Severe or medically significant but not immediately life-threatening; hospitalization or prolongation of hospitalization indicated; disabling; limiting self-care ADL. (Self-care ADL refer to bathing, dressing and undressing, feeding self, using the toilet, taking medications, and not bedridden.)
- Grade 4: Life-threatening consequences; urgent intervention indicated.
- Grade 5: Death related to AE

Treatment-Emergent Adverse Events

A TEAE is any event that was not present prior to the initiation of study drug or any event that worsens in either intensity or frequency following exposure to study drug.

Collecting and Recording Adverse Events

AEs spontaneously reported by the patient and/or in response to an open question from the study personnel or revealed by observation will be recorded in the EDC.

Information about AEs/SAEs will be collected from the first treatment through 30 days after the last dose of study drug or until alternate anticancer treatment has been initiated (whichever occurs earlier).

The AE term should be reported in standard medical terminology when possible. For each AE, the investigator will evaluate and report the onset (date and time), resolution (date and time), intensity, causality, action taken, serious outcome (if applicable), and whether or not it caused the patient to discontinue the study.

Concomitant illnesses that existed before entry into the study will not be considered AEs unless the illness worsens during the Treatment Period. Pre-existing conditions will be recorded as medical history in the eCRF.

Reporting Disease Progression

The event of disease progression is an efficacy criterion and is therefore not considered an AE. Disease progression should be reported within the EDC. If AEs/SAEs occur in relation to disease progression, the AEs/SAEs must be reported per AE/SAE reporting requirements.

Memorial Sloan Kettering Cancer Center
[name]
[name]

Follow-Up of Adverse Events

Investigators must follow subjects with AEs/SAEs until event resolution or stabilization, withdrawal of consent, subject loss to follow-up, or death, whichever occurs first.

If an investigator becomes aware of an SAE after the specified follow up- period and considers the SAE related to the study drug, the investigator should report the SAE to SpringWorks according to timelines for reporting SAEs.

Withdrawal due to Adverse Events

Withdrawal due to AEs should be distinguished from withdrawal due to other causes, according to the definition of AE noted earlier, and recorded on the appropriate AE eCRF page. When a patient withdraws because of an SAE, the SAE must be reported in accordance with the reporting requirements.

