14.3 Safety Analysis

All AEs will be listed, including the verbatim description per CTCAE v5.0. This analysis will be done on the safety population.

TEAEs are defined as those occurring after the first dose of study drug and within 30 days following the cessation of treatment, whether or not they are considered related to the study medication.

The following key safety parameters will be evaluated:

- Incidence of TEAEs, treatment-related TEAE, TEAEs leading to death, SAE, treatment-related SAE, TEAE leading to study drug discontinuation, TEAE leading to dose modifications (e.g., dose reduction) and TEAE leading to study discontinuation
- TEAEs will be further summarized by severity (according to NCI CTCAE Version 5.0)
- Changes in clinical laboratory parameters (hematology, chemistry, urinalysis), CTCAE graded laboratory toxicities, vital signs, ECOG performance status, ECG parameters, physical examinations, ophthalmology examinations, and usage of concomitant medications

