15.1 Serious Adverse Event (SAE) Reporting

An adverse event is considered serious if it results in ANY of the following outcomes:

- Death
- A life-threatening adverse event
- An adverse event that results in inpatient hospitalization or prolongation of existing hospitalization
- A persistent or significant incapacity or substantial disruption of the ability to conduct normal life functions
- A congenital anomaly/birth defect
- Important Medical Events (IME) that may not result in death, be life threatening, or require hospitalization may be considered serious when, based upon medical judgment, they may jeopardize the patient or participant and may require medical or surgical intervention to prevent one of the outcomes listed in this definition
- *List any additional events that require SAE reporting (pregnancy, AEs of special interest (AESI), secondary malignancies, etc.)*

Note: Hospital admission for a planned procedure/disease treatment is not considered an SAE.

SAE reporting is required as soon as the participant starts investigational treatment/intervention. SAE reporting is required for 30-days after the participant's last investigational treatment/intervention. Any event that occurs after the 30-day period that is unexpected and at least possibly related to protocol treatment must be reported.

Please note: Any SAE that occurs prior to the start of investigational treatment/intervention and is related to a screening test or procedure (i.e., a screening biopsy) must be reported.

Memorial Sloan Kettering Cancer Center
[name]
[name]

All SAEs must be submitted in PIMS. If an SAE requires submission to the HRPP office per [IRB SOP RR-408 'Reporting of Serious Adverse Events'](#), the SAE report must be submitted within 5 calendar days of the event. All other SAEs must be submitted within 30 calendar days of the event.

The report should contain the following information:

- The date the adverse event occurred
- The adverse event
- The grade of the event
- Relationship of the adverse event to the treatment(s)
- If the AE was expected
- Detailed text that includes the following
 - An explanation of how the AE was handled
 - A description of the participant's condition
 - Indication if the participant remains on the study
- If an amendment will need to be made to the protocol and/or consent form
- If the SAE is an Unanticipated Problem

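### The Section 15.0 rule on pre-existing illness ends at the last dose and conflicts with the 30-day AE, TEAE and SAE windows, so worsening that begins after the last dose could go unrecorded

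*Combined protocol and SAP*

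**What the plan says.** The rule at issue is in Section 15.0, under Collecting and Recording Adverse Events: "Concomitant illnesses that existed before entry into the study will not be considered AEs unless the illness worsens during the Treatment Period". The next sentence sends pre-existing conditions to medical history in the eCRF. Section 15.0 does not define the Treatment Period. Section 4.2 does: "The treatment period will be from the first dose of the first study drug until the last dose of the last study drug".

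Other text sets a longer reach:

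- The AE definition in 15.0 includes "the deterioration of a pre-existing medical condition following or during exposure to a pharmaceutical product" and allows for events in washout periods.
- The TEAE definition in 15.0 includes "any event that worsens in either intensity or frequency following exposure to study drug", with no end date.
- The collection rule in 15.0 reads "Information about AEs/SAEs will be collected from the first treatment through 30 days after the last dose of study drug", closing sooner if alternate anticancer treatment begins.
- Section 14.3 says "TEAEs are defined as those occurring after the first dose of study drug and within 30 days following the cessation of treatment", with no mention of alternate anticancer treatment.
- Section 15.1 says "SAE reporting is required for 30-days after the participant's last investigational treatment/intervention". Section 15.2 also records SAEs, related or not, for 30 days.

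On visits, Section 4.2 says "An End of Treatment (EoT) visit will be performed within 7-14 days after the administration of the last dose of the last study drug" and places the safety follow-up visit at 30 days. The Schedule of Assessments (Table 3) marks toxicities at both.

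**The concern.** Table 1 makes the type, incidence and severity of AEs a primary endpoint in both arms. A rule that decides whether something is an AE therefore acts on the primary endpoint at the point of recording. An event that the site files as medical history never reaches the 14.3 analysis.

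The rule concerns patients whom the trial admits. Sections 6.1 and 6.2 allow mild, controlled macular degeneration, treated hypertension, Grade 1 residual toxicity and, at the investigator's discretion, Grade 2 neuropathy. Drug exposure also outlasts the last dose: Section 3.1 gives the active metabolite a half-life of 30 to 40 hours. Worsening that starts in the following days may thus be drug-related.

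Any error runs one way, towards fewer AEs. It could also reach SAEs, because 15.1 defines a serious event as an adverse event with one of the listed outcomes. If worsening is not an AE, a hospitalisation for it is, on a literal reading, not an SAE.

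**Working it through.** The plan gives no figure to reproduce. The check is to compare how long after the last dose each rule counts worsening of a condition present at entry.

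| Rule | Where | Reach after the last dose |
|---|---|---|
| Pre-existing illness | 15.0, read with 4.2 | 0 days |
| AE definition | 15.0 | continues, no end stated |
| TEAE definition | 15.0 | continues, no end stated |
| AE/SAE collection | 15.0 | 30 days, or to alternate anticancer treatment if earlier |
| TEAE window | 14.3 | 30 days |
| SAE capture | 15.1, 15.2 | 30 days |

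Three cases, with no new anticancer treatment started:

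1. A baseline condition begins to worsen 10 days after the last dose. The pre-existing illness rule says it is not an AE. The AE definition and the collection window say it is, and 14.3 makes it a TEAE. The rules conflict.
2. A baseline condition begins to worsen in the last week of treatment and is first noticed at the end-of-treatment visit. The rule turns on when the illness worsens, not on when someone sees it, so this is an AE under every rule.
3. A new condition begins 10 days after the last dose. The pre-existing illness rule does not apply, so this is an AE under every rule.

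Only case 1 is exposed. Its window is 30 − 0 = 30 days at most, and shorter where the 15.0 collection rule closes early.

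Could the Treatment Period mean something longer? Section 4.2 names three periods (screening, treatment and post-study follow-up), and both 4.2 and 11.10 put the end-of-treatment and 30-day visits in follow-up. A sentence in 11.8 mentions an end-of-treatment visit before entry into the Post-Treatment Period, which could be read as placing that visit inside treatment. Even then the period would extend only to day 7–14, leaving 30 − 14 = 16 to 30 − 7 = 23 days uncovered. Nothing extends it to day 30.

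Persistence of exposure: five half-lives of the metabolite are 5 × 30 = 150 to 5 × 40 = 200 hours, about 6 to 8 days. Five is the usual working convention, not a figure that the plan applies to this question.

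**The case against.** The strongest reply is that the rest of Section 15.0 already supplies the right answer. The AE definition and the collection window stand just above the disputed sentence, toxicities are scheduled at both post-dose visits, and a site would probably record the event. This stands in part: Section 15.0 contradicts itself, so under-counting is a risk under literal application, not a certainty. But the collection window says when AEs are gathered, while the disputed sentence says what counts as one. It is also the more specific rule and names another place to record the condition, so a site could reasonably follow it.

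The second reply is that test results do not need an AE label. Table 1 lists abnormal laboratory, vital-sign, ECG, LVEF, physical and ophthalmological findings as a separate primary component, and 14.3 summarises most of them. This stands for measured worsening, such as in the eye or in blood pressure. It does not cover symptomatic worsening, such as neuropathy, unless an examination registers it.

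A reader might infer that every finding of this type at the end-of-treatment and 30-day visits is lost. The documents do not support that, because the rule depends on onset. Suppose that a patient stops at the end of Cycle 4 and visits fall on nominal days. The previous eye examination was on Cycle 3 Day 1, 56 treatment days earlier, and the next comes 7 to 14 days after the last dose. Then 56/70 = 80% to 56/63 = 89% of the interval is on treatment. For a stop at the end of Cycle 3 the figures are 28/42 = 67% to 28/35 = 80%. Worsening found at that visit may well have begun on treatment.

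A reader might also take the 30 days as a share of the TEAE window, 30/(28c + 30) for c cycles: 30/86 = 35% at two cycles, 30/142 = 21% at four, 30/198 = 15% at six. These are calendar fractions under assumed durations. They are not shares of AEs, and they are upper limits where new anticancer treatment ends collection early.

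**Conclusion.** The inconsistency is real, and minor. One sentence in 15.0 excludes worsening of a baseline condition with onset after the last dose. The definitions and collection window in the same section, and those in 14.3, 15.1 and 15.2, include it for up to 30 days. If sites apply the sentence literally, AE counts and SAE capture could be too low for that class of event. The documents do not allow the number of events to be derived.

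The conclusion rests on two assumptions: that the capitalised term in 15.0 means the period defined in 4.2, which is the natural reading, and that some sites would put this sentence above the general AE definition. A claim that Section 15.0 as a whole stops counting at the last dose would go too far.

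Sample size, power and the 3+3 rules are unaffected. Cycle 1 DLT assessment is essentially untouched; the only conceivable overlap is a patient who stops treatment during Cycle 1.

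**What to change.** In 15.0, replace the reference to the Treatment Period in the pre-existing illness sentence with the section's own AE collection window: from first dose to 30 days past the last dose, ending sooner if alternate anticancer treatment begins.

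In 14.3, state that worsening of a pre-existing condition within that window is a TEAE. The same edit should settle whether alternate anticancer treatment closes the window: 15.0 says that it does, and 14.3 is silent. A flat 30-day wording in 15.0 alone would leave that difference in place.

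The cost is a phrase in 15.0 and a sentence or two in 14.3. The visits and toxicity checks are already scheduled. The only downside is that AE counts may rise slightly.
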